4.5.4 Radiotherapy Time and Dose Considerations

Fractionation

Patients will receive one RT treatment per day, 5 days per week. All fields will be treated each day. At least 2 fractions must be given during the first week of treatment.

4.5.5 Treatment Technique

Any 3D treatment technique which delivers the appropriate dose to the PTV is permitted. Coplanar and noncoplanar techniques are both allowed. A treatment planning

computerized-tomography (CT) scan is required. The MRI defined volumes should be superimposed onto the treatment planning CT.

Simulation

Simulation will be performed using a CT simulator.

Patient Position and Immobilization

Reproducible setups are critical and the use of immobilization devices such as thermoplast mask, bite-block, etc. should be used for all patients.

Field Shaping

Field shaping can be done with blocks or multi-leaf collimation

Isocenter verification

The equivalent of orthogonal (AP and lateral) digitally reconstructed radiographs (DRRs) and corresponding orthogonal weekly portal images (film or electronic) are required. Alternatively, image guidance with KV imaging and setup digital reconstructed radiographs or cone beam CT is acceptable.

4.5.6 Organs at Risk

Dosimetry constraints for organs at risk will be judged on the composite plan. When possible to do so without shielding gross tumor, attempts should be made to limit dose to the following structures:

Table 4 Dosimetry constraints for organs at risk

Organ	Dose limitation
Brainstem inferior to thalamus	1% or less receiving 54 Gy
Optic chiasm	1% or less receiving 54 Gy
Optic nerve	1% or less receiving 54 Gy
Globe or retina	1% or less receiving 50 Gy
Normal brain outside PTV1	Minimize volume receiving 5700 cGy

4.5.7 Radiotherapy Dose Calculation and Reporting

Isodose Distributions and Dose Volume Histograms

Selected 3DCRT cases and all IMRT cases will be electronically submitted for review according to details in the ABTC Radiation Oncology QA plan (www.abtconsortium.org). Hard copy plans will not need to be submitted. This electronic system will allow review of isodose lines and dose volume histograms.

IMRT Plan Verification

If IMRT is used, the monitor units generated by the IMRT planning system must be independently checked prior to the patient's first treatment. Measurements in a QA phantom can suffice for a check as long as the plan's fluence distributions can be recomputed for a phantom geometry. Treatment may proceed if the calculated dosimetric error is estimated to be 5% or less.

Digital Submission

Submission of treatment plans in digital format (either Dicom RT or RTOG format) is required for selected cases of 3DCRT and all cases of IMRT according to the ABTC Radiation Oncology QA plan (www.abtconsortium.org). The MRI (T1 post-contrast and T2/FLAIR), treatment planning CT, and DICOM-RT objectives utilized to generate the treatments will need to be digitally submitted including separate plans for PTV1, PTV2, and composite (sum) plan. Plans should be submitted within 14 days of the completion of radiation therapy.

Questions

Questions regarding the RT section of this protocol should be directed to:

4.5.8 Definitions of Deviations in Protocol Performance

The QA assessment of PTV coverage will be based upon the individual plans for PTV1 and PTV2. Normal tissue tolerance will be assessed based upon the composite (sum) plan.

Prescription Dose

Minor Deviation

The dose to the prescription point differs from that in the protocol by between 6% and 10%.

Major Deviation

The dose to the prescription point differs from that in the protocol by more than 10%.

Dose Uniformity

Minor Deviation

99% of the PTV receives less than 95% of the prescription dose, or more than 10% of the PTV receives more than 110% of the prescription dose

Major Deviation

80% of the PTV receives less than 95% of the prescription dose.

Dose and volumes deviations will not be scored if the normal tissue dosimetry in the Dose Calculation and Reporting section is the reason for the dose deviation.

Volume

Minor Deviation

Margins less than specified or fields excessively large as deemed by the study.

Major Deviation

Transection of tumor (GTV) or potentially tumor bearing area (CTV).

Phase I Study to Determine the Safety and Tolerability of the Oral Microtubule Destabilizer BAL101553 in Combination with Standard Radiation in Patients with *MGMT* Promoter Unmethylated Newly Diagnosed Glioblastoma

ABTC # 1601

NCI # ABTC-1601

PI: [name]

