4.5.3 Target Radiotherapy Dose

Prescription Point

For 3D treatment planning, the prescription point is at or near the isocenter. The goal of the treatment plan is to encompass at least 99% of the PTV within the 95% isodose surface. IMRT plans may be prescribed to an isodose line provided that dose uniformity guidelines are met.

Dose Definition

The absorbed dose is specified as cGy to muscle.

Tissue Heterogeneity

Calculations shall take into account the effect of tissue heterogeneities.

Total Dose

The total dose to the prescription point will be 6000 cGy in 30 daily fractions of 200 cGy each. PTV1 will receive 4600 cGy in 23 fractions. PTV2 will receive an additional 1400 cGy in 7 fractions (total 6000 cGy in 30 fractions).

Dose Uniformity

For conformal planning techniques (3D conformal and IMRT), the 99% PTV shall be encompassed within the 95% isodose surface and no more than 10% of the PTV should receive more than 110% of the prescription dose, as evaluated by dose volume histogram.

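### The PTV-coverage limb of the radiotherapy deviation definitions in protocol section 4.5.8 contradicts the coverage requirement in section 4.5.3 and, read literally, leaves most coverage failures unscored

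*Protocol*

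**What the plan says.** Protocol section 4.5.3 (Target Radiotherapy Dose) states the coverage standard twice. Under the prescription point: "The goal of the treatment plan is to encompass at least 99% of the PTV within the 95% isodose surface". Under dose uniformity, for 3D conformal and IMRT planning: "the 99% PTV shall be encompassed within the 95% isodose surface", with the companion limit that "no more than 10% of the PTV should receive more than 110% of the prescription dose". Both limits are judged on the dose volume histogram (DVH).

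Protocol section 4.5.8 (Definitions of Deviations in Protocol Performance) turns these limits into deviation classes:

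- Minor, low-dose limb: "99% of the PTV receives less than 95% of the prescription dose".
- Minor, high-dose limb: "more than 10% of the PTV receives more than 110% of the prescription dose".
- Major, low-dose limb only: "80% of the PTV receives less than 95% of the prescription dose".

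The section also says: "The QA assessment of PTV coverage will be based upon the individual plans for PTV1 and PTV2". A deviation is not scored when normal-tissue dosimetry is its cause. No other section of the protocol or SAP restates or corrects the coverage classes. The ABTC Radiation Oncology QA Plan is cited in sections 4.5 and 4.5.7 for accreditation and for plan submission and review, but it is not reproduced.

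**The concern.** A deviation scale built on a requirement should do two things: score every plan that misses the requirement, and give the more serious label to the larger miss. As printed, the low-dose limb does neither. Its minor class describes a target that is almost entirely underdosed, its major class a target that is somewhat less underdosed, and failures short of the major cut-off fall in neither class.

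The primary objective concerns the drug combined with standard radiation, so the record of how well that radiation was planned is part of describing what patients received. If reviewers apply the printed definitions, a plan that misses 4.5.3 by a wide margin can pass quality assurance with no coverage deviation. It may then not appear in the listing of reported protocol deviations (SAP section 5.1.2).

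**Working it through.** Let U be the percentage of the PTV that receives less than 95% of the prescription dose. Coverage is then V95 = 100 − U.

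**Step 1. The limb that agrees.** Section 4.5.3 allows at most 10% of the PTV above 110% of prescription. The complement is more than 10% above 110%, which is exactly the high-dose limb of the minor class in 4.5.8. The minor class therefore looks intended to capture failures of 4.5.3.

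**Step 2. The same derivation for coverage.** Section 4.5.3 requires V95 ≥ 99, that is U ≤ 1. The complement is U > 1. Section 4.5.8 instead prints 99% for minor and 80% for major, both as shares of the PTV that are *underdosed*. The printed cut-offs do not follow from the requirement.

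**Step 3. Classify by U.** The printed percentages carry no inequality sign; here they are taken as minimum cut-offs (minor U ≥ 99, major U ≥ 80). Three readings are compared:

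| U (%) | V95 (%) | 4.5.3 | Literal | Labels swapped | DVH shorthand |
|---|---|---|---|---|---|
| 1 | 99 | meets | none | none | none |
| 2 | 98 | fails | none | none | minor |
| 20 | 80 | fails | none | none | minor |
| 21 | 79 | fails | none | none | major |
| 60 | 40 | fails | none | none | major |
| 79 | 21 | fails | none | none | major |
| 80 | 20 | fails | major | minor | major |
| 98 | 2 | fails | major | minor | major |
| 99 | 1 | fails | minor and major | major | major |

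The DVH shorthand takes each line to mean that the dose covering 99% (or 80%) of the PTV is below 95% of prescription: minor when V95 < 99, major when V95 < 80.

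**Step 4. Results.**

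- Literal: every plan with 1 < U < 80 fails 4.5.3 and has no coverage deviation. At U = 60, only 100 − 60 = 40% of the target is covered and nothing is scored. On this limb, every plan that is minor (U ≥ 99) is also major (U ≥ 80), so no plan is minor alone. If the percentages are taken as exact values, the gap is wider.
- Labels swapped: the order is restored, but 1 < U < 80 is still unscored.
- DVH shorthand: U ≤ 1 none, 1 < U ≤ 20 minor, U > 20 major. No failing plan is unscored and the order is right. This shows that a reading consistent with 4.5.3 exists; it is not offered as the threshold to adopt.

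**Step 5. The other scales in 4.5.8.** Prescription-point dose runs from a 6–10% difference (minor) to more than 10% (major). Volume runs from margin faults (minor) to transection of tumor or tumor-bearing area (major). Only the coverage limb runs the wrong way.

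**The case against.** The best defence is that the wording is loose DVH language. Section 4.5.8 reuses both number pairs of 4.5.3 (99/95 and 10/110), so a radiation physicist might well read the minor line as failure of the 99% coverage standard and the major line as a larger failure. On that reading the conflict disappears. This is plausible and may be what was meant, but the text does not say it. It also requires one half of the sentence to be shorthand and the other half a plain volume share. A wording correction is needed either way.

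The consequences are limited, and these points stand:

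- A reader might infer that the quality-assurance rules cannot detect inadequate radiation. They can in part: prescription-point, hot-spot and volume deviations are still scored, 4.5.3 remains a requirement in its own right, and section 4.5.7 provides for review of isodose lines and DVHs for all IMRT and selected 3DCRT cases.
- A reader might infer that the MTD is compromised. Evaluability rests on a DLT after at least one dose, or on receiving at least 80% of the expected drug dose (protocol 4.2.2, SAP 3.4). The radiation stopping rule concerns completing at least 75% of RT (protocol 4.2.2 and 10.3). Neither uses the deviation classes.
- A reader might infer that OS and PFS are affected. They are descriptive Kaplan-Meier summaries in the safety population (SAP 5.2), and no analysis set excludes patients by RT deviation.
- SAP 5.4.2 reports RT duration, dose and percentage received regardless of 4.5.8, although these do not measure PTV coverage.
- SAP 5.1.2 lists reported deviations without referring to the 4.5.8 classes, so an effect on that listing is possible, not documented.

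**Conclusion.** The contradiction is real but confined to one limb of one scale. Taken literally, with the percentages as minimum cut-offs, section 4.5.8 assigns no coverage deviation to any plan with more than 1% and less than 80% of the PTV underdosed, although each fails 4.5.3, and its minor class is a worse underdose than its major class. That interval describes the rule; it does not say how often such plans occur.

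The tempting diagnosis is that the two labels were transposed. Step 4 rules that out as a sufficient explanation, since swapping leaves the gap intact. The likelier fault is that the share underdosed is stated where the share covered was meant. Nor do the documents show that any plan was mis-scored: how reviewers read the definitions, and what the external QA plan says, cannot be seen from here. The effect falls on radiotherapy quality assurance and on which RT deviations are reported, not on the MTD determination.

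**What to change.** The sponsor should reconcile the coverage limb of section 4.5.8 with section 4.5.3 so that every plan that misses 4.5.3 falls in a class and the major class is the more severe. The choice of thresholds is the sponsor's; none is proposed here. The hot-spot limb and the prescription-point and volume scales need no change on this account.

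The sponsor should then confirm in writing which reading the plan reviewers applied. If they scored failures of coverage in line with 4.5.3, a note to that effect is enough. If they used the literal wording, the electronically submitted plans should be re-scored for PTV1 and PTV2 separately and the deviation listing updated before database lock.

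The cost is small: a wording correction and one query to the reviewers. Any re-scoring is bounded by the 26 patients given in SAP section 2.4.2 and uses plans already held in digital form. Because only selected 3DCRT cases are submitted, re-scoring may not reach every patient, and the study report should say so.

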4.6 General Concomitant Medication and Supportive Care Guidelines

Patients may receive other medications that the Investigator deems to be medically necessary, with the specific exception of non-protocol-specified chemotherapy, RT, anti-neoplastic biological therapy, or other investigational agents. Patients who require the use of any of the aforementioned treatments for clinical management should be removed from the study.

4.6.1 Prohibited Concomitant Medication during Study

There must be a period of at least 10 days from discontinuation of prohibited drugs and initiation of therapy unless otherwise specified in the protocol. Requests for specific exceptions to the required wait time can be submitted to the ABTC Central Office by providing a pharmacological rationale that the washout period for a particular drug should be less than 10 days (or as specified in the protocol); this must be approved by the ABTC Central Office.

Patients on drugs that are strong inhibitors and/or inducers of CYP2C9, CYP2C19 or CYP3A4 (including EIAEDs; see [Appendix IV](#)), are not eligible for enrollment or treatment under this protocol. Patients taking non-EIAEDs (see [below](#)) are permitted to take part in the study. Patients previously treated with EIAEDs, or any of the prohibited concomitant medications listed in [Appendix IV](#), may be enrolled if they have been off the medication for ≥ 10 days prior to the first dose of BAL101553.

Concomitant use of BAL101553 with P-gp substrates should be avoided if possible. In cases where the concomitant use of BAL101553 with P-gp substrates cannot be avoided, patients should be carefully monitored for clinical signs of toxicity (see [Appendix IV](#) for additional recommendations).

Coumarin derivates (including warfarin potassium, phenprocoumon or acenocoumarol) **are not permitted**. Other anticoagulant treatments (including heparin, low-molecular weight heparin, direct thrombin/factor Xa inhibitors, aspirin, or other oral platelet inhibitors such as clopidogrel) are allowed.

Enzyme-Inducing Anti-Epileptic Drugs (EIAED)

For this study, patients may not be on EIAEDs, such as phenytoin; patients who require anti-epileptic drugs (AED) may be on non-EIAEDs (NEIAEDs). If a patient on this study protocol needs to have an AED started or needs to have a second AED added then only NEIAED should be used. There must be a ≥ 10 day period from discontinuation of an EIAED and initiation of therapy. In the event that an ELAED must be used for a patient on study, the patient will be removed from the protocol.

Drugs that are strong inhibitors and/or inducers of CYP2C9, CYP2C19 and CYP3A4

In vitro studies suggested a potential for interactions in drug metabolism between BAL27862, the active component of BAL101553, and concomitant use of drugs interfering with CYP2C9 (and to a lesser extent with CYP3A4 and CYP2C19). Patients using concomitant medications known to be strong inhibitors and/or inducers of CYP2C9,

CYP2C19 and CYP3A4 (see [Appendix IV](#)) will be excluded from participating in the study.

Herbal and Non-Traditional Medications

No data exist regarding the interaction of BAL101553 with commonly-used herbal or non-traditional medications. Patients should be instructed not to use such medications while receiving BAL101553 therapy. The intake of St. John's Wort is prohibited under this protocol (see [Appendix IV](#)).

4.6.2 Permitted use of Prophylactic/Supportive Concomitant Treatments

Antiemetics

Prophylactic antiemetic treatment is not primarily recommended. However, once a patient has experienced \geq CTCAE grade 1 nausea or vomiting this patient may then receive prophylactic antiemetic therapy at the discretion of the Investigator. Patients taking antiemetic treatment prior to the study may continue their treatment at the discretion of the Investigator.

Antidiarrheal treatment

The use of antidiarrheal treatment should be commenced at the first sign of abdominal cramping, loose stools or overt diarrhea. Diagnosis and appropriate management of diarrhea is mandatory.

Bisphosphonates

Bisphosphonates may be continued or initiated at the discretion of the Investigator. A dental examination and appropriate preventive dental care should be available or should be performed, and renal function should be carefully monitored.

Corticosteroids

Postoperatively, corticosteroids should be tapered to a stable dose as determined by the clinical status of the patient. The lowest required steroid dose should be maintained throughout the duration of the study in order to eliminate steroid effects as a confounding variable in the interpretation of serial brain-imaging studies. Corticosteroid doses can be tapered as clinically indicated if the patient appears to be responding to therapy, as judged by serial scans. Corticosteroid dose may, of course, be increased in the event of clinical deterioration or at the discretion of the attending physician. In the event of suspected clinical deterioration, repeat brain imaging is recommended.

Blood pressure elevations

Prophylactic antihypertensive treatment is not primarily recommended. If transient BP elevations are observed following administration of oral BAL101553, the administration of short-acting antihypertensive drugs (such as labetalol or captopril) should be considered. See [Table 5](#) below for details.

Patients may also receive chronic antihypertensive treatment (e.g., long-acting calcium channel blockers, ACE-inhibitors, angiotensin receptor blockers, thiazide diuretics or beta blockers). Additional short-acting antihypertensive medication may be given as add-on therapy (on an "as needed" basis).

Patients who experience symptomatic BP elevations (e.g., symptoms consistent with hypertensive encephalopathy, suspected intracerebral hemorrhage, stroke or transient ischemic attack, acute myocardial infarction, acute left ventricular or dissecting aortic aneurysm) should be managed and treated according to institutional standards of care.

Table 5 Blood Pressure Requirement for Initiation and Continuation of BAL101553 Dosing

Systolic BP	Diastolic BP	
< 140 mmHg	< 90 mmHg	Required for patient eligibility at Screening
< 160 mmHg	< 100 mmHg	Required on study to continue long-term study treatment
< 180 mmHg	< 110 mmHg	Required to continue dosing
Recommended Interventions Related to Blood Pressure		
BP	Time point	Recommended Intervention
SBP \geq 140 mmHg or DBP \geq 90 mmHg	Screening	Patient ineligible unless repeat BP measurements are SBP < 140 mmHg AND DBP < 90 mmHg.
SBP \geq 160 mmHg or DBP \geq 100 mmHg (confirmed upon repeated measurements)	Any post-Screening study visit day	Initiate antihypertensive treatment or modify existing treatment to achieve SBP < 160 mmHg AND DBP < 100 mmHg within 1 week.
SBP \geq 180 mmHg or DBP \geq 110 mmHg (confirmed upon repeated measurements)	Any post-Screening study visit day	Withhold dose until SBP < 160 mmHg AND DBP < 100 mmHg.
Any recording of SBP > 220 mmHg or DBP > 110 mmHg	Any post-Screening study visit day	DLT: withhold dose until SBP < 160 mmHg AND DBP < 100 mmHg; then reduce dose by one level.
SBP \geq 160 mmHg or DBP \geq 100 mmHg that persists for > 1 week despite antihypertensive treatment	Any post-Screening study visit day	DLT: withhold dose until SBP < 160 mmHg AND DBP < 100 mmHg; then reduce dose by one level.
Grade 4 hypertension	Any post-Screening study visit day	DLT: discontinue patient from study.

5.0 DOSE MODIFICATION FOR TOXICITY

5.1 Dose Limiting Toxicity

A DLT is defined as a clinically-significant AE or abnormal laboratory value assessed as unrelated to disease progression, intercurrent illness, or concomitant medications and meets any of the criteria below. Any DLT must be a toxicity considered at least possibly related to BAL101553 or the combination of BAL101553 and radiation.

Treatment-related DLTs are defined below. Dose limiting toxicities must have an attribution of possible, probable, or definite to BAL101553 or the combination of BAL101553 and radiation. For patients experiencing a DLT, BAL101553 will be interrupted. If the patient recovers (\leq grade 1 [or tolerable grade 2 for non-hematologic toxicity] or \leq baseline), a BAL101553 dose reduction (1 dose level reduction) is required for subsequent doses. Skipped BAL101553 doses will not be made up. If there is any question or clarification required concerning a potential DLT, the treating site should contact the ABTC Central Office to determine patient's DLT status. The ABTC Central Office, with the Study Chair, will make the final decision.

➤ **Hematological toxicities** will be considered dose limiting if any of the following occur and complete blood counts and differentials were obtained according to the mandated schedule (CBC, differential, and platelets drawn twice a week until the ANC \geq 1500/mm³ and platelets \geq 100,000/mm³):

- ANC of $<$ 500/mm³.
- Platelets $<$ 25,000/mm³.
- Febrile neutropenia
- Any hematological toxicity that prevents administration of \geq 80% of the planned BAL101553 dose

Grade 3 or 4 lymphopenia will not be considered a DLT.

➤ **Central nervous system toxicities**

- \geq **Grade 2** central nervous system (CNS) ischemia will be considered a DLT
- \geq **Grade 2** neurological toxicities that interfere with activities of daily living and do not resolve spontaneously or with steroids, anticonvulsants, or electrolyte correction within 2 weeks will be considered a DLT
- Symptomatic CNS hemorrhage of any grade will be considered a DLT.

➤ **Grade 3 and 4 non-hematological, non-CNS toxicities** will be considered dose limiting with the following exceptions:

- Grade 3 nausea, vomiting, or diarrhea without sufficient prophylaxis with a duration $<$ 3 days;
- Alopecia;
- Grade 3 fatigue;
- Grade 3 hyperglycemia that is reversible and without clinical symptoms;
- Grade 3 electrolyte disturbances that are asymptomatic and reversible within 3 days, and do not re-occur upon continuing or re-initiation at the same dose;
- Grade 3 or 4 hypophosphatemia, unless considered clinically relevant;
- Grade 3 or 4 elevations in alkaline phosphatase;
- Grade 3 hypertension that resolved to \leq Grade 2 hypertension within 1 week either spontaneously or upon implementation of antihypertensive therapy

ABTC # 1601

NCI # ABTC-1601

PI: [name]

- A subject's first episode of deep venous thrombosis (DVT) or pulmonary embolism will not require dose modification.
- **Any adverse event that leads to missing > 6 doses of BAL101553** will be considered dose limiting.
- **Any recording of SBP > 220 mmHg or DBP > 110 mmHg or any Grade 4 hypertension** will be considered dose limiting.

ANY DLT (AS DEFINED ABOVE) CAUSING DELAY IN TREATMENT OF OVER 7 DAYS WITHOUT RECOVERY TO A \leq GRADE 1 OR BASELINE STATUS WOULD RESULT IN TAKING THE PATIENT OFF TREATMENT.

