4.4.1 BAL101553 Administration

Oral BAL101553 should be taken on an empty stomach, after a period of fasting of at least 4 h. Patients should refrain from food intake for at least 1 h after drug administration. Intake of water is permitted at any time.

Patients should take their BAL101553 dose at approximately the same time each day. BAL101553 should be taken about 1 hour before each weekday session of RT.

If the duration of RT exceeds 6 weeks, then treatment with BAL101553 should be stopped after 49 days.

If a dose of BAL101553 is missed due to reasons other than toxicity, the missed dose can be taken later in the same day, as long as the patient is able to observe the fasting requirements. If the patient cannot follow the fasting guidelines, or cannot take the dose for reasons other than toxicity, the dose will not be replaced (i.e., patients should not take more than one day's dose on any given calendar day). Should a patient miss a scheduled dose due to vomiting, the patient should not re-take the dose and should wait until their next scheduled dose.

Starting Dose

BAL101553 will be administered on an outpatient basis, once daily as an oral dose of 4 mg, for 6 continuous weeks during RT.

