4.4.2 Drug dispensing to patients

New study drug will be dispensed to patients at study visits at weekly intervals. All safety parameters (including laboratory safety parameters and MMSE[®]) applicable for assessing the ability for a patient to continue receiving study medication must be reviewed at any study visit prior to dispensing new study medication.

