9.3.3 SAE Reporting

Any SAE, as described in Section [9.3.1](#), including death due to any cause, which occurs during this study must be **reported immediately (within 24 hours)** to the ABTC Central Office.

A phone call must be made to:

ABTC Manager: [REDACTED]

Basilea will be responsible for reporting of any SAE to the FDA as required by legislation. Basilea will notify the FDA of any unexpected, fatal or life-threatening experience (expedited report) associated with the use of study drug as soon as possible but no later than 7 calendar days after the initial receipt of the information. Initial notification will be followed by a written report within 15 calendar days. For other unexpected serious events (i.e. that are not fatal or life-threatening) associated with the use of study drug, Basilea will notify the FDA as soon as possible, but no later than 15 days, of the initial receipt of information.

These events also must be reported by the Investigator to the appropriate IRB.

Patients who are removed from study due to AEs should be followed until the AE has resolved or stabilized. Copies of relevant documentation, such as laboratory reports, should be kept with the patient's study records.

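### Protocol 5.1 as worded can leave two narrow kinds of related dose-limiting toxicity uncounted when six or fewer doses are missed

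*Protocol*

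**What the plan says.** Under Protocol 5.1 a DLT must be attributable to BAL101553, or to its combination with radiation, and must meet one of the listed criteria.

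- **Haematological.** These toxicities "will be considered dose limiting if any of the following occur and complete blood counts and differentials were obtained according to the mandated schedule". A parenthesis then describes twice-weekly draws until counts recover. The listed events are ANC <500/mm³, platelets <25,000/mm³, febrile neutropenia, and haematological toxicity that prevents 80% of the planned dose.
- **CNS.** Ischaemia of Grade 2 or higher, symptomatic haemorrhage of any grade, and unresolved neurological toxicity of Grade 2 or higher that limits daily activities.
- **Other.** "Grade 3 and 4 non-hematological, non-CNS toxicities", with a list of exceptions. One of these has no grade limit: "A subject's first episode of deep venous thrombosis (DVT) or pulmonary embolism will not require dose modification".
- **Catch-all.** "Any adverse event that leads to missing > 6 doses of BAL101553". This item has no blood-count condition and no grade limit.
- **Threshold rules.** Any SBP >220 or DBP >110 mmHg (5.1), hypertension persisting beyond 1 week despite treatment (Table 5), and sodium <130 mmol/L that is symptomatic, not reversible within 3 days, or recurrent (Table 7 note 13).

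Three safeguards surround the list. Safety parameters, including laboratory values, "must be reviewed at any study visit prior to dispensing new study medication" (4.4.2). Any SAE, "including death due to any cause, which occurs during this study must be" reported to the Central Office within 24 hours (9.3.3). On questioned cases, "The ABTC Central Office, with the Study Chair, will make the final decision" (5.1).

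The SAP adds no DLT definition of its own. SAP 2.2.1 makes the frequency and characteristics of DLTs the primary endpoint, and SAP 5.4.1 plans only a listing of the counted DLTs.

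**The concern.** Whether blood was drawn on time says something about data quality. It does not make an observed, attributable event less toxic. A missed draw can hide toxicity, but it should not cancel toxicity that was seen. The grading scale in Protocol 9.2.1 runs to Grade 5 (fatal), so naming only Grades 3 and 4 leaves out the worst grade. The CNS items in the same section are open-ended, so wider wording was available.

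Both omissions act in one direction. They can only lower the DLT count, so any resulting error pushes the selected dose upward. Decisions rest on 3 to 5 evaluable patients, so one event can be decisive. There is also a consequence for the patient: the mandatory interruption and one-level dose reduction in 5.1 and 5.2 are tied to DLT status.

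**Working it through.** The plan states no figure for this point, so there is none to reproduce. The check covers dose counts, the decision lists, and a labelled illustration.

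**1. How far the catch-all reaches.** Planned doses are 7 × 6 = 42 (Protocol 4.1). More than 6 missed means 7 or more. Evaluability without a DLT needs 80% of the expected dose (4.2.2): 0.80 × 42 = 33.6, so at least 34 doses. A patient who misses 6 has taken 36/42 = 85.7% and stays evaluable. The fourth haematological item needs 9 or more missed doses (42 − 33 = 9), so the catch-all already covers it.

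Radiotherapy may overrun: "If the duration of RT exceeds 6 weeks, then treatment with BAL101553 should be stopped after 49 days". Six missed of 49 leaves 43/49 = 87.8%, taking 49 as the denominator. The evaluability text refers only to the 6 weeks, so that denominator is an assumption; against 42 the share would be higher still.

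**2. Gap (a).** Take a related ANC <500/mm³ found when the twice-weekly repeat draws were not kept, with 6 or fewer doses missed. The haematological criterion fails on its second condition and the catch-all fails on the dose count. If the 10 weeks are completed, the patient enters the denominator as a non-DLT.

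**3. Gap (b).** Take a related, non-haematological, non-CNS death with no earlier qualifying Grade 3/4 record and no sodium or blood-pressure trigger. Only the catch-all could count it. With no earlier missed doses, a last dose on day d misses 42 − d doses:

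- day 35: 42 − 35 = 7, caught;
- day 36: 42 − 36 = 6, not caught.

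The exposed period is therefore at most days 36–70, or 35 of the 70 evaluation days. If dosing runs to day 49, it is days 43–70, or 28 of 70. What matters is doses missed because of the event, not the date of death: a patient who stops by day 35 for the toxicity and dies on day 60 is caught. These are calendar spans, not risks.

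**4. Effect of one lost DLT**, read from the lists in Protocol 11.1, with the patient still evaluable:

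| Observed | Counted | Decision |
|---|---|---|
| 1/3 | 0/3 | expand → escalate |
| 2/3 | 1/3 | de-escalate → expand |
| 2/4 | 1/4 | de-escalate → escalate |
| 2/5 | 1/5 | de-escalate → escalate |
| 1/4, 1/5 | 0/4, 0/5 | escalate, unchanged |
| 3/3, 3/4, 4/4, 3/5, 4/5, 5/5 | one fewer | de-escalate, unchanged |

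Four of the 12 outcomes change. In an expanded cohort, 3/6 (exceeded) becomes 2/6 (MTD) under Table 3. If a patient who died is instead judged non-evaluable, 2/4 becomes 1/3 (expand), 2/5 becomes 1/4 (escalate), and a three-patient cohort falls to 2 evaluable.

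**5. Illustration only.** The documents give no rate of lost DLTs. Let p be the true DLT rate, f an assumed fraction lost, q = p(1 − f), and take 5 evaluable patients. The chance of escalating is P(X ≤ 1) = (1 − q)⁵ + 5q(1 − q)⁴.

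| p | f = 0 | 1% | 2% | 5% | 10% |
|---|---|---|---|---|---|
| 33% | 46.8% | 47.4% | 48.1% | 50.1% | 53.4% |
| 40% | 33.7% | 34.4% | 35.1% | 37.2% | 40.9% |
| 50% | 18.8% | 19.4% | 20.0% | 22.0% | 25.6% |

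**The case against.** The strongest reply is that coverage is wider than a quick reading of 5.1 suggests, and much of that reply stands.

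- **Fatal events already caught.** CNS ischaemia, CNS haemorrhage and unresolved neurological toxicity are open-ended in grade. The sodium and blood-pressure rules are thresholds, which a fatal outcome does not undo. Hyponatraemia, a main severe signal with oral dosing (2.2, 6.1), is therefore largely covered. A reader might infer that related deaths in general are not DLTs, or that every death from day 36 on is missed. The documents do not support either.
- **Scope of the blood-count condition.** The parenthesis describes the twice-weekly repeat draws, which Table 7 note 2 triggers once counts are low. A reader might infer that any missed or late count voids a haematological DLT. That is only one reading; the clear case is a lapse in the repeat draws.
- **Recovery wording.** Section 5.1 joins the ANC and platelet thresholds with *and*; Table 7 note 2 and SAP Table 1 note 2 use *or*. A reader might see a further route to lost DLTs. The note can be read in line with 5.1, so this is only an ambiguity.
- **First DVT or pulmonary embolism.** If Grade 5 already lies outside the parent item, the exception removes nothing more today. It would matter once the parent item is extended to Grade 5.
- **Rarity and oversight.** For oral doses up to 16 mg/day, 6.1 lists only Grade 1/2 anaemia among blood-count effects, and the top dose here is 15 mg. Deaths reach the adjudicating office within 24 hours. The planned laboratory shift tables and related-death counts (SAP 5.4.3, 5.4.4) would show such events.

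This does not close the gaps. Adjudication applies the written rule and starts when a question is raised, and a literal reading of an off-schedule case may raise none. No planned output reconciles the safety tables with the DLT listing.

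**Conclusion.** The point holds in a limited form and is minor. Two kinds of related event can go uncounted as 5.1 is written, each only when 6 or fewer doses are missed: haematological events with off-schedule counts, clearly so for the repeat draws; and non-haematological, non-CNS deaths with no earlier qualifying Grade 3/4 record that escape the sodium and blood-pressure rules. Grade ≥3 was probably the intent for the second. The blood-count condition, by contrast, is an explicit added requirement.

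The average effect is small if losses are rare. The effect on a single cohort that loses a DLT can be a changed dose decision, at 1/3, 2/3, 2/4 or 2/5; that count holds for a DLT lost for any reason and is not specific to this wording. The 1–10% loss fractions are assumptions without a source in the documents, and so is the use of 5 evaluable patients. Nothing in the documents shows that such an event has occurred. A reader might infer that the MTD is biased, but the text supports only the possibility and its direction.

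**What to change.** In Protocol 5.1, delete the blood-count schedule condition so that any observed, attributable haematological event on the list counts. Change the non-haematological, non-CNS item to Grade ≥3, and state that no exception, including first DVT or pulmonary embolism, applies to a Grade 5 event. Using *and* for count recovery in Table 7 note 2 and SAP Table 1 note 2 is an optional tidy-up.

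SAP 2.4.2 reports 26 patients included, so the practical step is to check those cases. In SAP 5.4.1, add a listing of any related ANC <500/mm³, platelets <25,000/mm³, febrile neutropenia or related death within 10 weeks that was not counted as a DLT, with the reason.

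The cost is a short amendment and one listing. No new data are needed: SAP 5.4.4 already includes unscheduled laboratory values, and SAP 5.4.3 already tabulates related events leading to death. If an uncounted event is found, the decision at that dose level has to be read again. If none is found, the sponsor can record that the MTD does not depend on this wording.
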